5.1.3 Day 2 (Cycles 1 and 2)

The following procedures will be performed 24 hours after the end of infusion:

- 12-lead ECG.
- Sample collection for central laboratory analysis of PK parameters.
- Sample collection for cytokine analysis.

5.1.4 Day 3 (Cycles 1 and 2)

The following procedures will be performed 48 hours after the end of infusion:

- Sample collection for central laboratory analysis of PK parameters.
- Sample collection and shipment for central laboratory analysis of peripheral WBC populations (Part 2).

5.1.5 Day 5 (Cycles 1 and 2)

The following procedures will be performed 96 hours after the end of infusion:

- Sample collection for central laboratory analysis of PK parameters.
- Sample collection and shipment for central laboratory analysis of peripheral WBC populations (Part 2).

5.1.6 Day 8 (± 1 day) of Each Cycle

- Physical examination, including neurological examination and including whole-body skin assessment (Cycles 1 and 2). The examination must include a determination if the patient has had any infection. At the discretion of the investigator, evaluation of any reported infection must be conducted to rule out infection with a microorganism that may be associated with autoimmune or neurological disease(s) as specified in the exclusion criteria.
- Weight (Cycles 1 and 2).
- Vital signs.
- Hematology and biochemistry parameters.
- Urinalysis and sample collection for additional renal function studies.
- Sample collection for central laboratory analysis of PK (Cycles 1 and 2).
- Sample collection for central laboratory analysis of peripheral WBC populations (Part 2).
- Collection of AE information.
- Collection of concomitant medication information.

5.1.7 Day 19 (± 3 days) of Each Cycle

NOTE: If the timing of the assessments required at the Day 1 visit for the next cycle coincides with the Day 19 visit, assessments that are included at both Day 19 and Day 1 are to be performed only once.

- Physical examination, including neurological examination and including whole-body skin assessment for Cycles 1 and 2. The examination must include a determination if the patient has had any infection. At the discretion of the investigator, evaluation of any reported infection must be conducted to rule out infection with a microorganism that may be associated with autoimmune or neurological disease(s) as specified in the exclusion criteria.
- Weight and vital signs measurements (Cycles 1 and 2).
- Hematology and biochemistry parameters.
- Urinalysis and sample collection for additional renal function studies.
- Sample collection for central laboratory analysis of PK (Cycles 1 and 2).
- Sample collection for central laboratory analysis of peripheral WBC populations (Part 2).
- Collection of AE information.

- Collection of concomitant medication information.

5.1.7.1 Bone Marrow Aspirate or Biopsy

A BMA (or biopsy if aspirate unattainable) will be obtained at the Day 19 visit (± 3 days) of each cycle, beginning with Cycle 2, and repeated at each subsequent cycle, until disease progression, CR (Section 7.1), or CRi is achieved. Once CR/CRi is achieved, sampling will be repeated at least every 3 cycles, or, as clinically indicated.

A bone marrow sample (aspirate or biopsy if aspirate unattainable) will also be collected at the EOT Visit (Section 5.1.8) for those patients who have not demonstrated disease progression and if their most recent sample was obtained more than 12 (± 1) weeks prior to the EOT Visit.

Response to treatment with ADCT-301 (Section 7.1) is to be performed by an approved clinical laboratory.

5.1.8 End of Treatment Visit

The following procedures will be performed within 30 days (+ 7 days) after treatment discontinuation:

- Serum or urine pregnancy test.
- Physical examination, including neurological examination and including whole-body skin assessment. The examination must include a determination if the patient has had any infection. At the discretion of the investigator, evaluation of any reported infection must be conducted to rule out infection with a microorganism that may be associated with autoimmune or neurological disease(s) as specified in the exclusion criteria.
- Weight and vital signs measurements.
- ECOG performance status.
- Hematology, coagulation panel, and biochemistry parameters.
- Urinalysis and sample collection for assessment of additional renal function studies.
- 12-lead ECG.
- Sample collection for central laboratory assessment of PK, soluble CD25, ADA, and cytokines.
- Sample collection for central laboratory analysis of peripheral WBC populations (Part 2).
- Collection of AE information.
- Collection of concomitant medication information.
- Bone marrow sample (see Section 5.1.7.1).

5.1.9 12-Week Follow-up Visit

Each patient will have a sample taken for assessment of PK and ADA at 12 weeks (± 1 week) after their last dose of ADCT-301.

Blood Sample Collection and Adverse Event Monitoring During Long-Term Follow-up

For all patients, a PK and ADA blood sample collection will be performed 12 weeks (± 1 week) following the last dose of ADCT-301.

For all patients, collection of AEs and SAEs will continue for 84 days (12 weeks) after the last dose of study drug or initiation of new anti-cancer treatment (see [Section 7.3.2.2](#)).

5.1.10 Long-term Follow-up

Patients who discontinue treatment for any reason other than disease progression will continue to be followed by telephone contact approximately every 12 weeks from the last disease assessment until disease progression or initiation of new anti-cancer treatment. After documentation of disease progression or start of new anti-cancer treatment, patients will be followed (by telephone contact or chart review) approximately every 12 weeks for up to 12 months after the last dose of study drug to collect survival information.

5.2 Withdrawal of Patients from the Study

The duration of the study participation for each patient is defined as the time from the date of signed written informed consent through the completion of the follow-up period or withdrawal of consent.

5.2.1 Reasons for Withdrawal/Discontinuation

Patients may withdraw from treatment at any time and for any reason, without prejudice to their future medical care. Patients may also be withdrawn by the Investigator or others at the study site.

A patient may be withdrawn from treatment for any of the following reasons:

- Disease progression.
- AE.
- Withdrawal of consent.
- Major protocol deviation.
- Required treatment delay >21 days (except in case of potential patient benefit, which must be approved by the Sponsor).
- Non-compliance, including lost to follow-up.
- Pregnancy.
- Other (e.g., development of contraindications).

- The Investigator determines it is in the best interest of the patient to discontinue the patient's participation in the study.
- Discontinuation of the study by the Sponsor.
- Death.

Note: Patient enrollment will be halted, pending a safety analysis and review with the appropriate regulatory authority(ies), if any patient in Part 1 or Part 2 experiences a CTCAE Grade 5 AE, or 2 non-hematologic CTCAE Grade 4 AEs, which are not attributable to the underlying disease, and for which relationship to ADCT-301 cannot be ruled out, within 30 days of their last dose of ADCT-301.

Note: Patients who experience a DLT during Cycle 1 are to be permanently discontinued from the study.

5.2.2 Handling of Withdrawals

The Investigator will confer with the Sponsor if a patient experiences a serious or intolerable AE. If a patient discontinues from the study because of an AE, the patient will be followed to satisfactory resolution, until the Investigator deems the event to be chronic or not clinically significant, or until the patient is considered to be stable ([Section 7.3.2.6](#)).

For each patient who discontinues study treatment and withdraws from the study, the Investigator will record the reason(s) for discontinuation on the relevant page of the electronic case report form (eCRF). Whenever possible, each patient who discontinues study treatment will undergo an EOT Visit and all EOT assessments ([Section 5.1.8](#)). Patients who fail to return for final assessments are to be contacted by the investigative site. Following a minimum of two documented unsuccessful telephone calls, the investigative site will send a registered letter to the patient in a final attempt to ensure protocol compliance.

Note: Once discontinued from the study, for any reason, patients are not permitted to be re-enrolled into the study.

5.2.3 Patient Replacements

Any patient in Part 1 who discontinues before completion of the first treatment cycle, for any reason other than a DLT, is to be replaced.

6 Study Treatments

6.1 Method of Assigning Patients to Treatment

In Part 1 (dose-escalation), patients will receive an IV infusion of ADCT-301 according to their assigned schedule.

The first patient at each new dose level must be observed for 7 days for occurrence of AEs prior to treating the second patient at that dose level. Patients will be entered sequentially to each dose level. The dose-escalation procedure is described in [Section 4.1.1](#).

In Part 2, (expansion), all patients will be assigned to the dose level of ADCT-301 identified in Part 1 by the DESC. Once the recommended Part 2 dose is determined, patients receiving lower dose levels of ADCT-301 may be offered continued treatment at the recommended dose.

6.2 Prophylactic Treatments for Hypersensitivity

If 1 patient experiences a CTCAE Grade 2 or higher infusion-related hypersensitivity reaction ([Appendix 13.2](#)) at any time during Part 1 (dose-escalation), all subsequent patients must receive prophylactic treatment, as described below or as per the institution's standard of care, to reduce the risk of hypersensitivity reactions.

- On Day 1 of each cycle, patients will be instructed to take 20 mg orally of dexamethasone, at 12 and 6 hours before the start of ADCT-301 infusion. When necessary, 12 and 6 hours before the first infusion may be defined as “immediately before sleeping” and “immediately after waking up.”
- On Day 1 of each cycle, patients will be given 50 mg IV of diphenhydramine hydrochloride at 30 minutes before the start of ADCT-301 infusion.
- On Day 1 of each cycle, patients will be given 50 mg of ranitidine (or equivalent) IV at 30 minutes before the start of ADCT-301 infusion.
- For 2 days following administration of ADCT-301 on Day 1, all patients are to take dexamethasone 4 mg orally, twice per day.

Other doses and other medications for prophylaxis and treatment of hypersensitivity or infusion reactions may be administered, according to standard treatment center protocols. Medications for the treatment of severe hypersensitivity reactions, including anaphylaxis, should be available for immediate use.

If a patient experiences a CTCAE Grade 1 or 2 hypersensitivity reaction, the following medications (or equivalent) should be administered for 48 hours after ADCT-301 infusion:

- Ranitidine 150 mg orally, 2 times per day.
- Diphenhydramine hydrochloride 50 mg orally, 3 times per day.

Any patient who experiences a CTCAE Grade 3 or higher hypersensitivity reaction ([Appendix 13.2](#)) should be discontinued from the study and immediately treated according to institutional standard of care and determined by the treating Investigator. These patients must be carefully observed after the treatment. Additional therapy, as per the institution's standard of care, should also be followed.

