No more than 9 additional patients (e.g., 3 cohorts of 3 patients) will be enrolled in the remaining dose escalation portion of this study (max. dose level 50 µg/kg/week) from the date of protocol amendment number 5, unless 2 additional patients attain a PR, CR, or CRi, in which case additional patients will be treated at a dose patients have cleared the DLT period, to determine if there is sufficient evidence of clinical activity to continue the study.

No more than 10 patients in total can be treated at any dose level unless ≥ 3 of the 10 patients have achieved a PR or better.

Every 3-Week Administration

Patients will be given ADCT-301 on Day 1 of each 3-week treatment cycle.

When the dose is escalated, the dose may increase by 100% if no DLTs are observed at the current level (e.g., at 6 µg/kg, the dose increase is 6 µg/kg). Once a DLT is observed at a given dose level, the next dose may only increase by 50% (e.g., at 6 µg/kg, the dose increase is 3 µg/kg). The dose may never increase by more than 100%, or more than an absolute value of 20 µg/kg at dose levels below 100 µg/kg and 50 µg/kg for dose levels between 100 and 150 µg/kg, whichever is less.

Weekly Administration

Patients will be given ADCT-301 (QW) on Days 1, 8, and 15 of each 3-week treatment cycle.

The first dose level for the QW dosing will be based on the safety and tolerability of patients who have been treated on the Q3W schedule. The first 3 patients will be given a cumulative dose each cycle that is comparable to (but not higher than) the highest dose tested at the Q3W dose schedule at which 3 patients completed the DLT observation period without a DLT. For example, if the highest Q3W dose tested at which 3 patients did not experience a DLT was cohort 92 µg/kg, the first cohort to receive (QW) dosing will receive 30 µg/kg each week for 3 weeks.

When the dose is escalated, the dose may increase by 50% if no DLTs are observed at the current level. Once a DLT is observed at a given dose level, the next dose may only increase by 25%. The dose may never increase by more than 50%, or more than an absolute value of 20 µg/kg/week, whichever is less.

A patient will maintain the same treatment schedule throughout the duration of the trial.

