5.1 Procedures by Study Day – Every 3-Week Dosing Schedule (Q3W)

The following procedures will be performed during the study. Regardless of dosing schedule, all patients will complete the same Screening procedures described in [Section 5.1.1](#), as well as the same procedures described for the End of Treatment (EOT; [Section 5.1.8](#)), 12-Week Follow-up Visit ([Section 5.1.9](#)) and Long-term Follow-up ([Section 5.1.10](#)).

Visit procedures described in [Section 5.1.2](#) – [Section 5.1.7](#) are for patients on the Q3W Schedule.

The Schedule of Procedures for the Q3W and QW dosing schedules are shown in [Table 1](#) and [Table 3](#), respectively, in [Appendix 13.1](#). Timings for sample collections for assessment of PK, ██████████ and other parameters for the Q3W dosing schedule are shown in [Table 2](#), and Cycle 1 and Cycle 2+ of the QW dosing schedule in [Table 4](#) and [Table 5](#), respectively, in [Appendix 13.1](#).

For QW dosing, most of the assessments will remain uniform with the Q3W dosing assessments, with the following exceptions:

- Study drug administration will occur at Days 1, 8, and 15
- The Q3W Day 19 assessments will be performed on Day 15 (concurrently with the 3rd QW dose) for the QW patients
 - Note: Bone marrow aspirate (BMA) or biopsy for QW patients is still performed at Day 19 ± 3 days but must be performed prior to the first dose of the next cycle.
- Pharmacokinetic and Pharmacodynamics, ADA, serum CD25 (sCD25), WBC population, cytokines, and additional renal function studies sampling schedule is adjusted according to the prescribed dosing schedule.

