6.4 Dose Delays and Modifications

Patients will receive the first 2 cycles, irrespective of blood count recovery. For patients achieving a CR/CRi, the subsequent cycle would be delayed until peripheral blood count recovery (absolute neutrophil count [ANC] $>0.5 \times 10^9/L$ and/or platelets $>50 \times 10^9/L$).

The Investigator should suspend ADCT-301 dosing for up to 21 days for any patient who experiences a protocol-defined DLT during any treatment cycle. At the discretion of the Investigator, the dose may also be delayed for up to 21 days for any toxicity that does not meet DLT criteria. Resumption of dosing with ADCT-301 after suspension is at the discretion of the Investigator, based on assessment of the patient's clinical condition and whether or not the patient is deriving potential clinical benefit from treatment with ADCT-301. Following recovery to CTCAE Grade 1 or to baseline grade, treatment with ADCT-301 may resume at the Investigator's discretion.

Patients who resume treatment following a dose delay may, at the discretion of the Investigator, have their dose reduced by 1 dose level. If toxicity recurs at a severity that would mandate a dose delay, then the dose may be further reduced 1 dose level. If toxicity recurs at such level, then the patient is to be discontinued from treatment. Dose re-escalation is allowed at the Investigator's discretion, at maximum to the dose level the patient was initially assigned to.

Dosing frequency may be adjusted according to individual patient response as described in [Section 4.1.1](#).

Patients experiencing certain types of infection during the course of participation in this clinical study also must delay further dosing, as stipulated in [Section 7.3.4.5](#).

Patients experiencing any autoimmune toxicities (e.g., endocrinopathies) \geq grade 1 need to be followed at least weekly to quickly detect deterioration and modify dosing as per DLT criteria (can be done by telephone unless symptoms worsen).

Patients who experience a DLT ([Section 7.3.1.1](#)) during Cycle 1 are to be permanently withdrawn from the study. Patients who experience the following significant toxicities will be immediately and permanently withdrawn from treatment with ADCT-301:

- Any patient who experiences a CTCAE Grade 3 or higher hypersensitivity reaction, regardless of premedication, during any cycle of treatment ([Appendix 13.2](#)).

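### Once triggered, the itemised hypersensitivity prophylaxis in Protocol 6.2 names Day 1 only, so on the weekly schedule it requires premedication before 1 of 3 infusions per cycle

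*Protocol*

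**What the plan says.** **The mandate.** Protocol 6.2 is triggered by a single Grade 2 or higher infusion-related hypersensitivity reaction in Part 1. From then on, "all subsequent patients must receive prophylactic treatment, as described below or as per the" institution's standard of care. The two routes are offered as equals, and 6.10.2 repeats the mandate by pointing back to 6.2.

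**The itemised route.** It has four elements:
- oral dexamethasone at 12 and 6 hours before the infusion, on Day 1;
- diphenhydramine: "On Day 1 of each cycle, patients will be given 50 mg IV of diphenhydramine hydrochloride", 30 minutes before the infusion;
- IV ranitidine 50 mg at the same time, on Day 1;
- oral dexamethasone afterwards: "For 2 days following administration of ADCT-301 on Day 1".

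**Other provisions in 6.2.** One is permissive: "Other doses and other medications for prophylaxis and treatment of hypersensitivity or infusion reactions may be administered". Another applies to a patient who has had a Grade 1 or 2 reaction, for whom "the following medications (or equivalent) should be administered for 48 hours after ADCT-301 infusion".

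**The weekly schedule.** Protocol 4.1.1 states: "Patients will be given ADCT-301 (QW) on Days 1, 8, and 15 of each 3-week treatment cycle". The list of QW exceptions in 5.1 repeats the dosing days ("Study drug administration will occur at Days 1, 8, and 15") and does not mention premedication. The only visible premedication line in the visit procedures is in the Day 1 list of 5.1.2, which applies to Q3W patients and refers back to 6.2.

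**The consequence of a severe reaction.** Protocol 6.4 requires permanent withdrawal from treatment for "Any patient who experiences a CTCAE Grade 3 or higher hypersensitivity reaction, regardless of premedication, during any cycle of treatment".

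**The concern.** The itemised regimen reads as a Q3W rule: one infusion per cycle, on Day 1, with premedication around it. Applied to QW without adaptation, it gives weekly patients less cover per infusion than Q3W patients, under a mandate that starts only because a reaction has already been seen.

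The two antihistamines are the clearest case. Each is timed 30 minutes before an infusion, and a QW cycle has three infusions, yet each item names only the first. A weekly patient who has a Grade 3 or higher reaction on Day 8 or Day 15 must leave treatment, possibly after an infusion for which the itemised regimen, followed exactly, required no premedication.

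**Working it through.** The plan states no coverage figure, so there is none to reproduce. The check is a count of infusion days against the days named in 6.2.

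**Inputs**
- Infusions per 21-day cycle: Q3W 1 (Day 1); QW 3 (Days 1, 8, 15). Source: Protocol 4.1.1.
- Infusion days named by the itemised regimen: Day 1 only, for all four elements. Source: Protocol 6.2.
- Patients first entered at a dose level: 3. Source: Protocol 4.1.1.

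**Required cover per cycle** = infusion days named ÷ infusions given
- Q3W: 1 ÷ 1 = 100%
- QW: 1 ÷ 3 = 33%

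**A QW cohort of 3 in Cycle 1**, with the trigger already met and every infusion given
- Infusions: 3 × 3 = 9
- Covered: 3 × 1 = 3
- Without required premedication: 9 − 3 = 6

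**Does anything given around Day 1 carry over?**
- Post-dose dexamethasone covers the 2 days after Day 1, so it ends on Day 3.
- The oral course after a Grade 1 or 2 reaction lasts 48 hours; after a Day 1 reaction it also ends on Day 3. It treats a patient who has already reacted and is not general premedication.
- Interval to the Day 8 infusion: 8 − 3 = 5 days. To the Day 15 infusion: 15 − 3 = 12 days.

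**Do other clauses require Day 8 and Day 15 cover?**

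| Clause | Allows it | Requires it |
|---|---|---|
| Standard-of-care route (6.2) | Yes | No; names no days |
| Other doses and medications (6.2) | Yes | No |
| Medication for the patient's welfare (6.10.2) | Yes | No |
| Dose-Escalation Steering Committee (DESC) dexamethasone options (6.10.2) | Week 1 only | No |

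**Effect of the fix.** Antihistamine cover on QW becomes 3 ÷ 3 = 100%. Itemised dexamethasone cover stays at 1 ÷ 3. Q3W is unchanged.

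**The case against.** **The table that might settle it is not visible.** Protocol 5.1 refers QW patients to Table 3, which is not shown in the text reviewed. A premedication row for Days 8 and 15 may be there. This stands. A reader might infer that the whole QW plan lacks premedication on those days, and the documents do not support that. The point is limited to the wording of 6.2, which would need to be brought into line with such a row if one exists.

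**The mandate is wider than the four items.** Standard of care is an equal route, other prophylaxis is allowed, and drugs for severe reactions should be at hand. This also stands. It would be wrong to infer that weekly patients are denied cover, or that any site left it out. The gap arises only at a site that takes the itemised route literally and uses none of the discretionary clauses.

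**Day 1 only may be deliberate.** One DESC dexamethasone option in 6.10.2 is confined to Week 1/Day 1 on any schedule, and the other to Week 1, Days 1 and 2. So a Day 1 steroid limit may be intended, and nothing here shows it to be an error. Neither option mentions the antihistamines. That silence does not prove an oversight: the protocol splits some procedures by schedule in its body text (weight, 7.3.6) and not others (ECG, 7.3.5).

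**The consequence is speculative.** The documents do not show that the trigger was met, give no reaction rate, and do not show that extra antihistamine would prevent a Grade 3 reaction. Nor are the infusions like for like: in the 4.1.1 example, the weekly dose is 30 µg/kg against 92 µg/kg on Q3W. All of this stands. A reader might go on to infer that the DLT assessment or the MTD is distorted; the documents do not support that.

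**Little practical use remains.** SAP 3.3 records that the trial ended before dose escalation was complete. This lowers the urgency but does not change what 6.2 requires.

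**Conclusion.** The point holds as a minor wording problem worth considering. Once the Grade 2 trigger is met, the itemised route in 6.2 requires premedication before 1 of 3 infusions per QW cycle, against 1 of 1 on Q3W. For a QW cohort of 3 in Cycle 1, that leaves 6 of 9 infusions without required premedication.

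This rests on three conditions: the trigger has been met, the site uses the itemised route rather than its standard of care, and it adds nothing under the discretionary clauses. It concerns the text of 6.2 and is subject to what QW Table 3 says. The size is a count of infusions; no change in reaction risk can be estimated from the documents. Confidence is medium.

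**What to change.** In Protocol 6.2, change the timing of the diphenhydramine and ranitidine items from Day 1 of each cycle to: *before every ADCT-301 infusion (Day 1 on Q3W; Days 1, 8 and 15 on QW)*. Align QW Table 3 and the QW exceptions in 5.1 if they do not already say this.

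Leave both dexamethasone items unchanged, with any steroid on Days 8 and 15 left to the DESC. Writing a Day 1 limit for every schedule into those items would harden a restriction that 6.2 does not justify. Leave the standard-of-care alternative as it is.

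**Cost**
- Two edits in 6.2, plus up to two alignments, made through a protocol amendment (11.2.1).
- Per QW cycle: 2 extra infusion days × 2 drugs = 4 extra IV doses. Each drug goes from 50 mg to 3 × 50 = 150 mg.
- For a cohort of 3 in Cycle 1: 4 × 3 = 12 extra doses.
- Some antihistamine sedation on Days 8 and 15. No extra steroid.

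If Day 1 only was intended for the antihistamines on QW, one sentence in 6.2 saying so would remove the ambiguity instead.
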